 a) Vascular endothelial cell protein expression and J wire collection procedure. Endothelial cells will be collected from an antecubital vein, washed, isolated fixed to slides, and stained with primary and secondary (immunofluorescence) antibodies for quantification of NFkappaB, IkappaBalpha nitrotyrosine, AMPkinase expression. Briefly, under sterile conditions a CRU nurse will insert an 18G catheter into an antecubital vein followed by a 0.018- or 0.021-inch mesh St. Jude 3 mm flexible guide wire (Daig Corp., Minnetonka, MN) with a J-shaped tip that is advanced 3-4 cm into and retracted 2-3 times through the catheter. The CRU nurse practitioner will be trained by the PI by watching a detailed video of the procedure and instructed by the PI who has observed >100 of these procedures at the University of Colorado-Boulder Clinical Translational Research Center between 2005-2009. The distal portion of the wire is then transferred to a 50-ml conical tube containing a buffer solution. Cells will be taken to the PIs lab (522 Field House) and cells are recovered by centrifugation and fixed to poly-lysine slides with formaldehyde and frozen at -80C until analysis. After blocking non-specific binding sites with 5% donkey serum (Jackson Immunoresearch), cells will be incubated with monoclonal antibodies for proteins of interest and a specific AlexaFlour488-conjugated secondary antibody (Research Diagnostics). Slides are then cover slipped with a VECTASHIELD DAPI (4',6'diamidino-2-phenylindole hydrochloride) fluorescent mounting medium (Vector Labs) and stored at 4 degrees C overnight. Slides are viewed using a fluorescence microscope (Eclipse 600, Nikon) and 30 individual endothelial cell images are digitally captured by a Photometrics CoolSNAPfx digital camera (Roper Scientific). These

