endothelial cells are documented by cell staining of vWF and nuclear integrity is confirmed using DAPI staining. Once endothelial cells with intact nuclei are identified, they were analyzed using Metamorph Software (Universal Imaging; Downingtown, PA) to quantify the intensity of primary antibody-dependent AlexaFlour488 staining (i.e., average pixel intensity). The number of cells typically recovered from each guide wire results in approximately 50-100 cells per slide. Eight slides and two control cultured human umbilical vein endothelial cell (HUVEC: passage 6-9 processed identically to the sample cells) slides are selected for each staining batch. Values are reported as a ratio of sample endothelial cells to HUVEC average pixel fluorescence intensity to reduce variability between staining batches. A singe technician will be blinded to the identity of the subject during the staining and analysis procedures.

- b) Pulse wave velocity. Carotid-femoral, carotid-brachial, and carotid-radial PWV will be measured non-invasively by recording carotid, femoral, brachial and radial artery pressure waveforms sequentially with an applanation tonometer (Non-invasive Hemodynamics Workstation, Cardiovascular Engineering, Inc.). Pressure waveforms are gated to the ECG R wave in order to calculate the transit time (t) between the foot of the carotid and the respective peripheral (femoral, brachial, radial) waveforms. The carotid-femoral transit distance (CFTD) is estimated between the 2 anatomical sites as the difference between the suprasternal notch (SSN) to carotid (SSN-C) and femoral (SSN-F) sites. Thus, the CFTD is calculated as CFTD= (SSN-F)-(SSN-C) and PWV calculated as CFTD/t. This approach accounts for parallel transmission of the pulse wave up the brachiocephalic and carotid arteries, and simultaneously along the aortic arch using the SSN as a fiducial point where parallel transmission begins (e.g., bifurcation site of aortic arch and brachiocephalic artery). The intra-subject reproducibility of carotid-femoral PWV is excellent with a coefficient of variation of 2.1% for triplicate measurements on non-consecutive days in 7 young adults.

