### X.4 How will information/data be collected and stored for this study (check all that apply):

- Paper/hard copy records (hard copy surveys, questionnaires, case report forms, pictures, etc.) - All hard copies of records will not contain any personal identifiers but only an individual subject code. Folders will be kept in a folder to keep out of public view when transported from CRU to the coordinagtors office. Data folders will contain hard copies of data capture forms such as surveys and data collected during experimental visits. All data folders will be kept in folder and locked in storage cabinet in the coordinators office (C-44 GH). The office is locked when the coordinator is not in the office. Signed informed consent documents and will be kept in a separate folder in a different locked file cabinet in the office.
- Electronic records (computer files, electronic databases, etc.) Data will be
  entered using subject ID code into the ICTS REDCap web-based database
  application that is password protected. No personal identifiable data will be
  entered. Only research staff on the IRB approved study will be allowed access
  this database. The ICTS REDCap staff are responsible for maintaining security
  of the data. Some data using subject ID code will also be entered into a
  Microsoft Excel and SPSS datasheets that will be kept in a shared server for

CLAS that is password protected. Only research staff on the IRB approved study will have access to the folder the study on the server. This server is maintained by [name], IT Support Services, College of Liberal Arts and Sciences.

- Name [name]
- Title IT Support Services II, College of Liberal Arts and Sciences
- University/VA Job Classification IT Support Services II
- Biologic samples (blood draws, check swabs, saliva samples, tissue samples, etc.) Basic blood chemistries will be sent to the UIHC pathology lab for analysis. Remaining biological specimens such as blood, endothelial cells, and DNA will be labeled with subject code, date collected and IRB protocol number and transported from the CRU to the PIs laboratory (522 Field House) in a secure unbreakable biohazard container. Samples will be stored in the PIs laboratory in a -80C freezer in N400 FH. All samples will be labeled with date collected and subject ID code only. No personal identifiable information will be labeled on the sample. Only the PI and his research staff will have access to the samples.
  - Name [name]

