### XI. Data Analysis

### XI.1 Describe the analysis methods you will use, including, if applicable, the variables you will analyze

Statistical analyses. To determine if differences in outcomes are present at baseline between obese pre-diabetic vs. non-pre-diabetic groups, an independent two-sample t-test will be performed. To determine if baseline (pre-intervention) differences exist between salsalate and placebo prediabetic groups after randomization, independent two-sample t-tests will be performed. To test the main hypotheses, a repeated measures ANOVA will be performed in which treatment (salsalate vs. placebo) is the between-subjects factor, and time (pre- vs. post-intervention outcomes) is the within-subjects factor for the primary dependent variables. The critical test for the dependent variable will be the interaction between the within-subjects and betweensubjects factors. Tests for mean contrasts will be used to compare variables of interest pre vs. post Salsalate or placebo. Based on a previous study, we expect small reductions in fasting glucose, triglycerides, LDL cholesterol and possibly systolic blood pressure after Salsalate treatment. Covariates (e.g., variables that change after Salsalate) will be included into the mixed model. Bivariate pearson correlation analysis will be performed on the change in each dependent variable and aforementioned selected covariates after Salsalate.

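### Endothelial-cell staining: the technician is masked to subject identity only, and code-plus-date labels could let visit order be inferred while 30 of about 50-100 cells are imaged

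*Combined protocol and SAP*

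**What the plan says.** Section VII.E.6, Experimental Methods for Visit 3, item a, gives one masking rule for the assay: "A singe technician will be blinded to the identity of the subject during the staining and analysis procedures". Cells are fixed to slides and frozen until analysis, and then "30 individual endothelial cell images are digitally captured". The yield is put at "approximately 50-100 cells per slide". A cell must stain for vWF and have an intact nucleus; no other rule says which 30 are taken. Software measures average pixel intensity, reported as a ratio to cultured control cells.

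Section X.4 describes the labels: "Remaining biological specimens such as blood, endothelial cells, and DNA will be labeled with subject code, date collected and IRB protocol number". It adds: "All samples will be labeled with date collected and subject ID code only". Neither section describes re-coding slides before staining or imaging.

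Section XI.1 makes the treatment-by-time interaction the critical test. It also plans contrasts within each arm: "Tests for mean contrasts will be used to compare variables of interest pre vs. post Salsalate or placebo". A two-sample t-test compares prediabetic and non-prediabetic subjects at baseline. Section XI.2 names carotid-femoral pulse wave velocity as the primary outcome.

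**The concern.** Masking to identity is not the same as masking to visit. If the label stays readable on the slide, the later of two dates under one code marks the sample taken on treatment. Intensity is measured by software, so the room for judgement lies in which cells are imaged. With 30 to 60% of the cells on a slide captured and no stated order, a technician who expects lower NFkappaB after treatment could drift, without intent, towards dimmer cells at the later visit.

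The pre v post contrasts within arm would absorb such a drift directly. They would then appear to support NFkappaB inhibition in vascular cells, the mechanism on which the trial's rationale rests.

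**Working it through.** The plan gives no figure for this point, so there is none to reproduce. The main check is textual; the arithmetic only shows what is possible.

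**1. What could be inferred**

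| Question | Documents | Reading |
|---|---|---|
| Is the technician masked to visit? | VII.E.6 item a: identity only | Not stated |
| What is on the specimen? | X.4: code, date, protocol number | No visit or group field |
| Does the label reach the slide? | Slides are frozen at -80C; X.4 labels the samples in that freezer | Likely, not stated |
| Does one person see both slides? | VII.E.6 item a: one technician | Yes, if all slides pass through that person |
| Are cells collected again after treatment? | Visit 6 repeats the Visit 3 vascular measurements; item g calls blood mononuclear cells a second cell type for verifying inhibition | Implied, not named |
| Is control status shown? | X.4: no group field; controls have no Visit 6 | At most a guess |

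On the guess: 15-20% attrition of 30 (XI.2) is 4.5 to 6 subjects. If every dropout lacked a second sample, controls would make up 10/(10 + 4.5) = 69% to 10/(10 + 6) = 63% of single-date codes, against 10/40 = 25% overall. Subjects still awaiting Visit 6 would lower that share.

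**2. Ceiling on the shift in one slide's mean**

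Suppose the brightest 30 of N cells were always taken and intensities were normal. The mean would shift by about φ(z)/p cell SDs, with p = 30/N and z = Φ⁻¹(1 − p). The finite-N values below are from simulation.

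| N | p | φ(z)/p | Simulated |
|---|---|---|---|
| 50 | 0.60 | 0.64 | 0.63 |
| 75 | 0.40 | 0.97 | 0.96 |
| 100 | 0.30 | 1.16 | 1.15 |

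This treats all 50-100 cells as eligible. If that count precedes the vWF and nucleus checks, the pool and the ceiling are smaller.

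**3. Weak selection (assumed inputs)**

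Take a correlation r of 0.1 to 0.3 between selection and brightness, and a cell-to-cell CV of 30 to 50%. Neither is in the documents. The shift is about r × ceiling: 0.1 × 0.63 = 0.06 SD up to 0.3 × 1.15 = 0.34 SD. As a share of the mean: 0.06 × 30% ≈ 2% up to 0.34 × 50% ≈ 17%. That is one slide. The same habit at both visits cancels in the change (zero); equal and opposite habits double it.

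**4. What a visit-related shift does to the planned tests**

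Let b be the shift in each subject's change, in SDs of change, equal in both arms. The salsalate mean change is Δs + b and the placebo mean change is Δp + b, so the interaction estimates Δs − Δp and b drops out. A within-arm contrast keeps b, with noncentrality b√n. In 40,000 simulated trials with no true effect (20 v 10, two-sided 0.05), rejection rates were:

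| b (assumed) | Interaction | Salsalate pre v post, n = 20 | Placebo pre v post, n = 10 |
|---|---|---|---|
| 0 | 4.9% | 5% | 5% |
| 0.25 | 5.0% | 18% | 11% |
| 0.5 | 5.0% | 56% | 29% |

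The documents give no SD of change for this assay, so the cell-level shifts in steps 2 and 3 cannot be converted into b.

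**5. Baseline comparison, only if control status were known**

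For 30 v 10, the noncentrality is b/√(1/30 + 1/10) = 2.74b on 38 degrees of freedom. False rejection would be 10% at b = 0.25 and 27% at b = 0.5, with b here in between-subject SDs. Step 1 shows that this condition is not established.

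**The case against.** The strongest reply is that silence is not evidence of unmasking. X.4 describes stored specimens, and no section says what the technician can read at the microscope. Since labels already omit names, masking to identity may have been meant to go further than the label. A single date does not reveal the visit; two dates under one code must be matched. Intensity is measured by software and scaled to control cells, and eligibility has two objective criteria. The trial is double-blind, the critical test is the interaction, and NFkappaB is also measured in blood mononuclear cells by an assay with no cell picking.

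Most of this stands, and it rules out several stronger readings that a reader might infer:

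- *That the technician knows pre from post.* The documents support only that it could be inferred.
- *That control status is visible.* The label has no group field, and a single date also fits a dropout or a pending Visit 6.
- *That scoring is subjective.* Only the choice of cells is open, and even that the technician makes the choice is an inference.
- *That the randomised comparison is compromised.* The safety report that the principal investigator supplies under VIII.4 contains unblinded salicylate data, but nothing says that the technician sees it.

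What the reply does not remove is the gap itself: masking to visit is not stated, re-coding is not described, and no order for picking the 30 cells is given. The software and the control-cell ratio act after the cells have been picked.

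**Conclusion.** The point holds as a cheap improvement to a secondary mechanistic assay. Stated masking covers identity only, labels carry code and date, and the choice of 30 cells has no fixed order, so visit order could be inferred while cells are being imaged. This rests on the label carrying over to the slide and on a repeat collection at Visit 6, both implied rather than stated.

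The analyses exposed are mainly the pre v post contrasts within arm; the baseline comparison with controls is exposed only if control status is guessed. The interaction is not biased provided that any shift is equal in both arms, and pulse wave velocity is unaffected. The size is unknown, with a lower bound of zero. The false-positive rates of 18% and 56% for the salsalate contrast follow from assumed shifts of 0.25 and 0.5 SD of change and are not estimates for this trial.

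**What to change.** - Before staining, have an existing lab member who does not score re-label every slide with a random code that hides subject code, date, visit and group. Open the key only after scoring is locked.
- In VII.E.6, Experimental Methods for Visit 3, item a, change the masking sentence so that the technician is blinded to subject, visit, group and treatment.
- In the same item, state that the first 30 vWF-positive cells with intact nuclei are imaged in a fixed scan order.

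The cost is one re-labelling step by existing staff, a small wording change, and a code key to maintain. If slides are already re-coded in practice, the change only documents it.

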| Approved Dose(s)  | 1 μg/mL/min intra-arterially for 6 min   |
| Approved Administration   | Intravenous, Other: intra-arterial via brachial artery   |
| Approved Dosing Regimen   | 0.3 μg/kg/min up to 10 μg/kg/min IV  |
| Is this study intended to be reported to the FDA as a well-controlled study in support of a new indication or a significant change in the labeling for this product?  | No   |
| Is this study intended to support a significant change in the advertising for this product?   | No   |
| Does this planned use of the product in this study, taking into consideration the route of administration, the dosage level, and the subject population, significantly increase the risk (or decrease the acceptability of the risk) associated with the use of this product? | No   |
| Rationale:  | Intra-arterial infusion at the proposed dose results in no change in systemic hemodynamics (e.g., heart rate and blood pressure). Raghuveer G, Sinkey CA, Chenard C, Stumbo P, Haynes WG: Effects of vitamin E on resistance vessel endothelial dysfunction induced by methionine. Am J Cardiol 88(3): 285-290; 2001.; 3) Gudmundson S, Sinkey CA, Chenard C, Stumbo P, Haynes WG: Resistance vessel endothelial function in healthy humans during transient postprandial hypertriglyceridemia. Am J Cardiol 85:381-385, 2000. |
|   | [name] et al. Hypertension 2008;52:72-79.  |

| Acetylcholine (Michol-E-System)  | pack)   |
|--|---|
| Name of Sponsor  |   |
| Investigator's Brochure Version  |   |
| Investigator's Brochure Date   |   |
| Planned Use in this Study  |   |
| Condition/Disease Indication(s)  | Forearm vascular endothelial dysfunction                |
| Subject Population   | Obese adults age 18-49 with prediabetes                 |
| Dose(s)  | 3-30 mcg/ml/min intra-arterially via brachial artery    |
| Administration   | Other: intra-arterial via brachial artery               |
| Dosing Regimen   | 3 mcg/ml/min for 6 min x 2; 30 mcg/ml/min for 6 min x 2 |
| FDA Approved Use   |   |
| Approved Condition/Disease Indication(s)   | vasodilation; gastorintestinal tract stimulant          |
| Approved Patient Population  | Adults  |
| Approved Dose(s)   | 30 mcg/ml/min   |
| Approved Administration  | Intravenous, Other: intra-arterial via brachial artery  |
| Approved Dosing Regimen  | 3 mcg/ml/min for 6 min x 2; 30 mcg/ml/min for 6 min x 2 |

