Drug infusion protocol: First, baseline FBF responses to intra-brachial artery infusions of 0.9% saline will be measured for 20 min at rate of 1 ml/min. Next, FBF responses during intra-brachial artery infusions of 2 incremental doses of the endothelial agonist acetylcholine (Ach; doses 3 and 30 mcg/min) or the endothelium-independent agonist sodium nitroprusside (SNP; doses 1 and 10 mcg/min) at 1 ml/min will be performed for 6 min for each dose. Both drugs will be diluted in 0.9% saline and sequence of Ach and SNP will be randomly assigned. FBF from each drug infusion will be recorded during the 3rd to 6th minute of each dose. A washout period of 0.9% saline at 1 ml/min will be performed for 20 min or less if FBF returns to baseline sooner. Next, the effects of oxidative stress on EDD will be determined by measuring the effect of ascorbic acid (vitamin C) infusion (25 mg/min) at an infusion rate 1 ml/min for a 10 minute loading dose prior to ACh infusion, and then continuous infusion throughout incremental infusion of AcH (doses 3 and 30 mcg/min). Specifically, any difference in the FBF response to ACh and the FBF response to ACh + vitamin C can be attributed to a reduction in vascular oxidative stress. SNP is used as an NO donor to test endothelium-independent dilation to establish that any observed group differences in Ach-mediated vasodilation is due, at least in part, to stimulated endothelial NO release per se, and not impairments in smooth muscle vasodilator function to an NO donor. Note: The concentrations selected for each of these agents have been shown to elicit changes in FBF without affecting systemic hemodynamics (i.e., no changes in heart rate or blood pressure).

b) Microneurography. Direct intra-neural recordings of sympathetic activity to skeletal muscle will be obtained using microneurography, as previously described. A tungsten micro electrode (200  $\mu$ m diameter shaft; 1-5  $\mu$ m uninsulated tip) is inserted into the peroneal nerve posterior to the head of the fibula. Well-validated criteria are used to

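### The within-session vitamin C contrast cannot be put down to oxidative stress: acetylcholine plus vitamin C is always the second, later acetylcholine exposure, with no repeat-acetylcholine control

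*Combined protocol and SAP*

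**What the plan says.** The Drug infusion protocol in VII.E.6 (Experimental Methods for Visit 4) sets out one session. A saline baseline comes first. Acetylcholine and nitroprusside follow at two doses each, and the "sequence of Ach and SNP will be randomly assigned". Each infusion "will be performed for 6 min for each dose", with flow read from the third to the sixth minute. A saline washout "will be performed for 20 min or less if FBF returns to baseline sooner". The vitamin C step comes after that: "Next, the effects of oxidative stress on EDD will be determined by measuring the effect of ascorbic acid (vitamin C) infusion", given "for a 10 minute loading dose prior to ACh infusion" and then continued through a second acetylcholine series.

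The inference is stated without conditions: any difference between the response to acetylcholine alone and "the FBF response to ACh + vitamin C can be attributed to a reduction in vascular oxidative stress".

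Four other places bear on this.
- The acetylcholine entry in V.8 lists "3 mcg/ml/min for 6 min x 2; 30 mcg/ml/min for 6 min x 2". That fits one series alone and one with vitamin C, and leaves none for a time control.
- The Visit 7 list in VII.E.6 says only that the Visit 4 measurements are done again. It is silent on infusion order.
- XI.1 makes the treatment-by-time interaction the critical test. It names neither the vitamin C contrast nor any order or period term.
- The ascorbic acid entry in V.8 and the Visit 4 list both include nitroprusside with vitamin C. The Drug infusion protocol omits it, and the Visit 4 list omits nitroprusside alone.

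**The concern.** Vitamin C and position in the session are the same variable in this design. Every subject receives acetylcholine alone first and acetylcholine with vitamin C later, so anything that changes the second response is counted as an effect of vitamin C. That could be drift in resting flow, a different response on repeat exposure, or residual effect of the preceding agent. Upward drift would imitate an oxidative-stress component, and downward drift would hide one. No analysis of the session data can separate these without a repeat acetylcholine run, and none is described.

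At stake is the mechanistic statement attached to the forearm flow study, which is one of the Aim 1 microvascular measures. As worded, the plan would let the baseline contrast alone support a conclusion about oxidative stress.

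**Working it through.** The documents give no effect size, SD or power for this contrast, so there is no planned figure to reproduce.

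**1. Is the position fixed?** The Drug infusion protocol, the Visit 4 list and the ascorbic acid entry in V.8 were compared. All three put acetylcholine with vitamin C after acetylcholine alone or describe it only as a later co-infusion. None adds a repeat acetylcholine run or a saline-for-vitamin-C run.

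**2. How far apart are the two acetylcholine series?** Inputs are 6 min × 2 doses = 12 min per agent, a washout of 0 to 20 min, and a 10 min vitamin C load.

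| Order | Start of acetylcholine alone to start of acetylcholine + vitamin C | Minutes |
|---|---|---|
| Nitroprusside first | 12 + (0 to 20) + 10 | 22 to 42 |
| Acetylcholine first, no washout between agents | 12 + 12 + (0 to 20) + 10 | 34 to 54 |
| Acetylcholine first, washout also between agents | 12 + 20 + 12 + 20 + 10 | up to 74 |

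The gap, and the agent given just before the vitamin C block, both depend on the random order.

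**3. What does each contrast estimate?** Let V be the vitamin C effect and T the combined effect of time, repeat exposure and residue.
- Within one session, the mean increment is V + T.
- Within one arm, the pre-to-post change is (V_post − V_pre) + (T_post − T_pre).
- Between arms, the difference in change is free of T if T is additive and alike in both arms.

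**4. How misleading could the within-session contrast be?** This is an illustration on assumed values: V = 0, SD of the one-visit contrast = 1, 20 salsalate and 10 placebo, 20,000 simulated trials, nominal 5% tests.

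| Assumed drift | Extra carry-over in one order | Baseline contrast significant | Interaction significant |
|---|---|---|---|
| 0 | 0 | 5% | 5% |
| 0.25 SD | 0 | about 26% | 5% |
| 0.5 SD | 0 | about 75% | 5% |
| 0.5 SD | 0.5 SD | about 97% | 5% |

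The mean of the interaction estimate stayed at about zero throughout.

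**5. What if the acetylcholine/nitroprusside order were redrawn at Visit 7?** The documents do not say that it is. Let e be the order effect in units of the SD of change. The change would shift by +e or −e with probability 1/4 each and by 0 with probability 1/2. The mean shift is 0 and the added variance is 0.5e². With 20% attrition the arms are 16 and 8:
- SE without an order effect: √(1/16 + 1/8) = 0.433
- e = 0.5: 0.433 × √(1 + 0.125) = 0.459, about 6% larger
- Range: e = 0.25 gives √1.03125 = 1.016 (about 2% larger), and e = 1 gives √1.5 = 1.225 (about 22% larger)

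**The case against.** **Vitamin C has to come last, because it could carry over into acetylcholine alone.** This stands as a reason for the order. The fault is the unconditional attribution combined with no time control, and the order itself need not change.

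**The planned test is already the right one.** XI.1 relies on the treatment-by-time interaction, which a common additive order effect does not bias. This is largely right and limits the point. But XI.1 does not name the vitamin C increment, and the attribution sentence in VII.E.6 is not restricted to the arm comparison.

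**Nitroprusside with vitamin C is a control.** Paired with nitroprusside alone, it could partly detect non-specific drift, though not a repeat-acetylcholine effect. The places that describe it disagree on whether both series are run, so it cannot be counted on as the text stands.

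**Oxidative stress is measured in other ways.** VII.E.6 also plans oxidised LDL, F2 isoprostanes and endothelial nitrotyrosine, and neither hypothesis in I.5 mentions oxidative stress. This lowers the weight of the contrast but does not make the sentence valid.

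A reader might also infer two stronger things that the documents do not support.
- **That the washout rule leaves the forearm dilated when the vitamin C block is read.** An early end to the washout requires return of flow to baseline. If flow has not returned, 20 min of washout, the 10 min load and a first reading in the third minute put 32 to 33 min between the previous agent and the first reading. Residual dilation is not excluded, but nothing shows that it is likely.
- **That a changed order at Visit 7 biases the treatment comparison.** The text is silent on any redraw, and a random redraw would add noise with mean zero.

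**Conclusion.** The concern holds for the attribution sentence. The within-session difference cannot separate vitamin C from time, repeat exposure or residual effect, whatever the sample size. How far it would mislead is unknown, because the documents give no drift; the 26% and 75% figures rest on assumed drifts of 0.25 and 0.5 SD.

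The reach is narrow. It affects a secondary mechanistic contrast, and the PWV primary outcome named in XI.2 is not involved. The salsalate-versus-placebo interaction is protected provided the order effect is additive and alike in both arms. That protection would weaken if salsalate itself altered the response to repeat acetylcholine. An order redrawn between visits would cost precision, about 6% in SE at an assumed e of 0.5. The point is worth correcting before analysis, but it does not threaten the trial's main comparison.

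**What to change.** - **Replace the attribution sentence.** Base the treatment-related oxidative-stress conclusion on the salsalate-versus-placebo difference in the pre-to-post change of the vitamin C increment, and name that increment in XI.1 as a variable for the interaction test. Describe the within-session difference as confounded with order.
- **State the reference flow.** Express each response relative to the flow recorded just before its block, and say whether for the vitamin C block this means before or after the load.
- **Assign the acetylcholine/nitroprusside order once per subject and keep it at Visits 4 and 7.** Balance of order within arm is not asked for: in the Visit 4 list the infusions (step c) come before treatment randomisation (step f), so the arm does not yet exist.
- **Reconcile the infusion descriptions.** The Drug infusion protocol, the Visit 4 list and the ascorbic acid entry in V.8 must agree on whether nitroprusside is given alone, with vitamin C, or both.

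No change to the washout rule is proposed. The cost is wording, one record of order per subject and no added infusion. The real downside is a weaker and less precise mechanistic claim. With 20 and 10 subjects and uncorrelated visits, the SE of the arm difference in change is √(2 × (1/20 + 1/10)) = 0.55 of the one-visit SD, against √(1/30) = 0.18 for the baseline contrast, so about three times as wide. Positive correlation between visits would narrow that gap.
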